## 13.4.3 Contraception Guidance

## **Contraception for Female (WOCBP) Participants**

Female participants of child-bearing potential must agree to use a contraceptive method that is highly effective, preferably with low user dependency, as listed below during the trial and at least 30 days following the last dose of TS-161.

## Contraceptives Allowed During the Study Include:

Highly Effective Methods That Have Low User Dependency

Failure rate of <1% per year when used consistently and correctly.

- Implantable progestogen-only hormone contraception associated with inhibition of ovulation
- Intrauterine device (IUD)

<sup>1 Contraceptive use by men or women should be consistent with local regulations regarding the use of contraceptive methods for those participating in clinical studies.

<sup>2 Failure rate of <1% per year when used consistently and correctly. Typical use failure rates differ from those when used consistently and correctly.

<sup>3 If locally required, in accordance with Clinical Trial Facilitation Group (CTFG) guidelines, acceptable contraceptive methods are limited to those which inhibit ovulation as the primary mode of action.

- Intrauterine hormone-releasing system (IUS)
- Bilateral tubal occlusion
- Vasectomized partner
  - Vasectomized partner is a highly effective contraceptive method provided that the partner is the sole sexual partner of the WOCBP and the absence of sperm has been confirmed. If not, an additional highly effective method of contraception should be used. Spermatogenesis cycle is approximately 90 days.

# Highly Effective Methods That Are User Dependent Failure rate of <1% per year when used consistently and correctly.

- Combined (estrogen- and progestogen-containing) hormonal contraception associated with inhibition of ovulation
  - Oral
  - Intravaginal
  - Transdermal
  - injectable
- Progestogen-only hormone contraception associated with inhibition of ovulation
  - Oral
  - Injectable
- Sexual abstinence

Sexual abstinence is considered a highly effective method only if defined as refraining from heterosexual intercourse during the entire period of risk associated with the study intervention. The reliability of sexual abstinence needs to be evaluated in relation to the duration of the study and the preferred and usual lifestyle of the participant.

**Note**: Periodic abstinence (calendar, symptothermal, post-ovulation methods), withdrawal (coitus interruptus), spermicides only, and lactational amenorrhoea method (LAM) are not acceptable methods of contraception. Male condom and female condom should not be used together (due to risk of failure with friction)

## **Contraception for Male Participants**

Male participants with a partner of child-bearing potential must agree to use following methods of contraception listed below from the initial administration of study intervention until at least 90 days following the last dose of TS-161.

## **Contraceptives Allowed During the Study Include:**

- Condom for male participant AND his partner of child-bearing potential must use one of the methods of contraception for female (WOCBP) participants (listed above)
- Sexual abstinence

Sexual abstinence is considered a highly effective method only if defined as refraining from heterosexual intercourse during the entire period of risk associated with the study

intervention. The reliability of sexual abstinence needs to be evaluated in relation to the duration of the study and the preferred and usual lifestyle of the participant.

**Note**: Male participants should refrain from fathering a child or donating sperm from the initial administration of study intervention until at least 90 days following the last dose of TS-161.

## 13.4.4 Collection of Pregnancy Information

## Male participants with partners who become pregnant

- The investigator will attempt to collect pregnancy information on any male participant's female partner who becomes pregnant while the male participant is in this study or prior to 90 days following his last dose of study intervention. This applies only to male participants who receive TS-161 (excluding placebo).
- After obtaining the necessary signed informed consent from the pregnant female partner directly, the investigator will record pregnancy information on the appropriate form and submit it to the sponsor within 24 hours of learning of the partner's pregnancy. Pregnancy of the participant's partner is not considered to be an AE, however, the female partner will be followed to determine the outcome of the pregnancy. Information on the status of the mother and child will be forwarded to the sponsor. Generally, the follow-up will be no longer than 6 to 8 weeks following the estimated delivery date. Any termination of the pregnancy will be reported regardless of fetal status (presence or absence of anomalies) or indication for the procedure. Any congenital anomaly must be reported as an SAE.

## Female participants who become pregnant

- The investigator will collect pregnancy information on any female participant who becomes pregnant while participating in this study. Information will be recorded on the appropriate form and submitted to the sponsor within 24 hours of learning of a participant's pregnancy.
- The participant will be followed to determine the outcome of the pregnancy. The investigator will collect follow-up information on the participant and the neonate and the information will be forwarded to the sponsor. Generally, follow-up will not be required for longer than 6 to 8 weeks beyond the estimated delivery date. Any termination of pregnancy will be reported, regardless of fetal status (presence or absence of anomalies) or indication for the procedure.
- While pregnancy itself is not considered to be an AE or SAE, any pregnancy complication or elective termination of a pregnancy will be reported as an AE or SAE. A spontaneous abortion or congenital anomaly is always considered to be an SAE and will be reported as such. Any post-study pregnancy related SAE considered reasonably related to the study intervention by the investigator will be reported to the sponsor as described in this appendix. While the investigator is not obligated to actively seek this information in former study participants, they may learn of an SAE through spontaneous reporting.
- Any female participant who becomes pregnant while participating in the study will discontinue study intervention or be withdrawn from the study.

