#### 2.3.1.9 Standard Treatment Phase

During the optional traditional standard treatment phase, participants may have worsening of symptoms, including suicidal ideation, as medications and dosages are adjusted. In addition, pharmacologic treatment may result in side effects.

At the end of study participation, patients with MDD will be offered short-term traditional standard treatment (up to two months). During this period, patients will be assessed and discussed at daily morning rounds by nursing staff and licensed independent practitioners (MD, APRN, part of the research team) for changes in psychiatric symptomatology and medication side effects. Additional interventions will be made depending on their status/progress. Additionally, our branch holds several weekly meetings to discuss our inpatients in the standard treatment phase, including an interdisciplinary treatment team meeting. During this meeting, ancillary team members not typically present at morning rounds (e.g., physical therapy, occupational therapy, pharmacy) will also have the opportunity to present their observations and weigh in on patient progress. If issues arise - for instance, psychiatric decompensation or intolerable side effects- medications may be adjusted/discontinued and/or additional medications or therapeutic interventions initiated based on a risk-benefit discussion between the inpatient treatment team and the patient. Additionally, if the patient expresses suicidal or homicidal thinking in the treatment phase, is judged to be an imminent risk of harm to self and/or others, and is not amenable to additional voluntary treatment on 7SE, he or she may be involuntarily psychiatrically hospitalized for his or her safety at an outside hospital.

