## 5 STUDY POPULATION

## 5.1 INCLUSION CRITERIA

In order to be eligible to participate in this study, an individual must meet all of the following criteria:

- 1. Ability of subject to understand and the willingness to sign a written informed consent document. To verify this, subjects must score ≥ 80% on the consent quiz (Appendix A).
- 2. Stated willingness to comply with all study procedures and availability for the duration of the study.
- 3. Aged 18 to 65.
- 4. Subjects must fulfill DSM-IV or DSM-5 criteria for MDD, single episode or recurrent without psychotic features, based on clinical assessment and confirmed by a structured diagnostic interview (SCID-P). Subjects must be experiencing a current major depressive episode of at least 4 weeks duration.
- 5. Subjects must have an initial score of  $\geq$  20 on the MADRS and a YMRS score of  $\leq$  12 within one week of the start of Phase I and upon entry into Phase II.
- 6. Ability to take oral medication and be willing to adhere to the TS-161 regimen.
- 7. Subjects must have a current or past history of lack of response to at least one adequate antidepressant trial (may be from the same chemical class) in the current major depressive episode, operationally defined using the modified-Antidepressant Treatment History Form (ATHF)); a failed adequate trial of ECT [or TMS] would count as an adequate antidepressant trial.
- 8. For females of reproductive potential: use of contraception starting at the time of enrollment and agreement to use such a method during study participation and for an additional 4 weeks after the end of Phase II (see Contraception Guidance, Appendix D).
- 9. For males of reproductive potential: use of condoms or other methods from the time of enrollment to ensure effective contraception with partner, and for an additional 90 days after the end of Phase II (see Contraception Guidance, Appendix D).
- 10. Agreement to adhere to Lifestyle Considerations throughout study duration

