# 8.7.8 Reporting of Pregnancy

Pregnant or nursing women or women who plan to become pregnant are excluded from this study. Participants who tested positive for pregnancy or become pregnant while enrolled in the study will be discontinued from the protocol and followed through pregnancy outcome.

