#### 10.5 SAFETY OVERSIGHT

This protocol will be reviewed by the NIMH-IRP Data and Safety Monitoring Board. The DSMB meets two times per year. The board will review study accrual and progress, adverse events related to the study, and safety and outcome data. Specific data elements required by the DSMB will be established at the first meeting the protocol is reviewed. The DSMB will have the authority to require changes in the study design, or to stop all or part of any study based on accumulating safety data.

The medically responsible investigator has the authority to break the blind in the event of an emergency. Breaking of the blind, life threatening injury or death all require immediate reporting to the DSMB and the NIMH Clinical Director. A written notification to the DSMB chair must follow within 7 days.

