## 13.4.2 Female participants

A female participant is eligible to participate if they are not pregnant or breastfeeding, and at least

- One of the following conditions, c) or d) applies:
  - a. Is not a WOCBP
  - b. Is a WOCBP and using a contraceptive method that is highly effective (with a failure rate of <1% per year), preferably with low user dependency, as described in this appendix, during the trial and for at least 30 days after the last dose of study intervention. The investigator should evaluate the effectiveness of the contraceptive method in relationship to the first dose of study intervention.
- A WOCBP must have a negative serum pregnancy test on Screening Visit and Day -1.
  - The investigator is responsible for review of medical history, menstrual history, and recent sexual activity to decrease the risk for inclusion of a woman with an early undetected pregnancy

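### Pregnancy collection for women stops at the end of participation, 28–29 days before the protocol's own contraception window closes, and the TS-161-only limit on partner pregnancies cannot be applied under the blind before crossover or to men who never cross over

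*Combined protocol and SAP*

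**What the plan says.** **Women, collection.** Section 13.4.4 reads: "The investigator will collect pregnancy information on any female participant who becomes pregnant while participating in this study". Section 8.7.8 says that participants who "become pregnant while enrolled in the study will be discontinued from the protocol and followed through pregnancy outcome". Neither adds any days after the last dose.

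**Women, contraception.** Inclusion criterion 8 (section 5.1, repeated in 5.6) asks for contraception "during study participation and for an additional 4 weeks after the end of Phase II". Section 13.4.2 (repeated in 13.4.3) asks for it "during the trial and for at least 30 days after the last dose of study intervention".

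**End of participation.** The Schedule of Events puts the last dose on Day 55 and the end of study on Day 56. Section 2.3.1.9 places the treatment phase after that: "At the end of study participation, patients with MDD will be offered short-term traditional standard treatment (up to two months".

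**Existing safety net.** Section 8.7.4 records non-serious AEs that start up to 7 days, and SAEs that start up to 30 days, after the last day of participation. Under 13.4.4 a pregnancy is in itself neither an AE nor an SAE. Miscarriage and congenital anomaly always count as SAEs, and complications and elective terminations are reported as one or the other. After the study, a pregnancy SAE judged related is reported if the investigator learns of it, with no duty to look for it.

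**Men.** Section 13.4.4 collects partner pregnancies during the study and up to 90 days after the man's last dose, with submission due within 24 hours of the investigator learning of the pregnancy. It then adds: "This applies only to male participants who receive TS-161 (excluding placebo".

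**Blind.** Sections 4.2 and 8.3 describe a double-blind crossover. Section 9.3 breaks the blind once accrual is complete. Section 10.5 lets the investigator break it in an emergency, and "Breaking of the blind, life threatening injury or death all require immediate reporting to the DSMB".

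**The concern.** Section 5.3.2 says that the safety of TS-161 in pregnancy is unknown, so any possibly exposed pregnancy carries information. For men, Appendix D makes the collection period and the contraception period equal, at 90 days after the last dose. For women, who take the drug themselves, the collection period has no tail at all.

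The male rule raises a different problem. Whether to collect depends on which treatment the man received, and the investigator is not meant to know this. In some situations the investigator must either leave a possibly exposed pregnancy uncollected or obtain an assignment. The second course matters because investigators adjust the dose while blinded (sections 4.2 and 6.1.2).

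**Working it through.** The plan gives no figure to reproduce. The check is day arithmetic on nominal schedule days, followed by a comparison of what is known about treatment at each stage.

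**Inputs.** Last doses on Day 20 (Condition 1) and Day 55 (Condition 2), end of study on Day 56 (section 1.3); windows of 4 weeks (5.1), 30 days (13.4.2) and 90 days (13.4.4); AE and SAE tails of 7 and 30 days (8.7.4); 20 of about 25 participants expected to cross over and complete (4.1).

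**1. Female gap for a completer.**
- By section 5.1, with Phase II ending on Day 56: 56 + 28 = Day 84; 84 − 56 = 28 days.
- By section 13.4.2: 55 + 30 = Day 85; 85 − 56 = 29 days.
- Men's partners, for comparison: 55 + 90 = Day 145.

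**2. What the safety net reaches.**
- Non-serious AEs: 56 + 7 = Day 63. SAEs: 56 + 30 = Day 86.
- The SAE tail therefore spans Days 57–85, but a pregnancy is not itself an SAE. A conception in that window with no SAE starting by Day 86 is not required to be collected. Its later outcome is reported only if it is an SAE, is judged related, and happens to become known.

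**3. The same gap counted from the last TS-161 dose.**
- TS-161 in Condition 2: last active dose on Day 55, so the full 29 days.
- TS-161 in Condition 1, completer: 20 + 30 = Day 50, which is 56 − 50 = 6 days before the end of study, so no gap.
- TS-161 in Condition 1, withdrawn on Day 34 (end of the two-week washout): 50 − 34 = 16 days. Withdrawn on Day 41 (34 + 7, after the extra washout week): 50 − 41 = 9 days.

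**4. Can the TS-161-only limit be applied under the blind?**

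| Situation of the man when the pregnancy is reported | Known to have received TS-161? | Limit usable under the blind? |
|---|---|---|
| In Condition 1 | No | No |
| In washout | No | No |
| Left before Condition 2 (dropout or sustained responder) | No | No |
| Dosed in both conditions, including the 90-day tail | Yes, whatever the sequence | Yes |

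In the first three rows submission is due within 24 hours, whereas planned unblinding waits for the end of accrual. Section 10.5 does not name a partner pregnancy as an emergency. Section 6.5 mentions an unblinded pharmacist, but no procedure has the pharmacist apply the limit, and telling the investigator whether to collect would disclose the assignment.

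**5. Size of the non-crossover group.** 25 − 20 = 5, and 5/25 = 20%. This covers both sexes and, by section 9.2, includes people lost in the drug-free period before any dose. The number of dosed men concerned would be smaller.

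**The case against.** The strongest reply is that very little is lost. Suppose, as an upper case, that all 25 participants are women of child-bearing potential. At the failure rate below 1% per year cited in Appendix D, the expected number of pregnancies in the gap is at most 25 × 0.01 × 29/365 ≈ 0.02. At an assumed 10% per year it is 25 × 0.10 × 29/365 ≈ 0.2. The two female contraception statements differ by only one day for a completer. All of this stands, and it limits the priority of the point. It does not make the rules consistent.

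Four stronger readings are tempting, and the documents do not support them.

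- **The male rule can never be applied without unblinding.** A man dosed in both conditions has certainly received TS-161, so the rule works for him.
- **The site is forced to break the blind in the remaining cases.** Section 13.4.4 does not forbid taking details from any man and applying the limit later. But it does not provide for that either, and the 24-hour deadline points to a decision at the time.
- **After participation only related pregnancy SAEs are reported.** Section 8.7.4 records SAEs for 30 days without requiring relatedness.
- **The last pregnancy test falls on Day 54, before the last dose.** The Day 56 footnote marker in the Schedule of Events is broken. The corresponding Day −1 entry carries the pregnancy-test footnote, so nothing can be concluded about testing on Day 56.

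**Conclusion.** The point holds as an inexpensive improvement, in two limited parts.

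For women, collection ends 28 to 29 days before the contraception window does. What is missed is chiefly a pregnancy conceived in that interval with no SAE by Day 86, together with its later outcome. This window is a contraception window; the documents do not call it an exposure window. Among completers the full gap follows actual TS-161 exposure only when TS-161 comes second.

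For men, the TS-161-only limit conflicts with the blind for pregnancies reported in Condition 1 or washout, and for men who never cross over.

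The day counts assume nominal schedule days, Phase II ending on Day 56, and participation ending before standard treatment, as section 2.3.1.9 implies. Few events are expected, and no endpoint, alpha or power figure changes.

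**What to change.** 1. In sections 13.4.4 and 8.7.8, extend collection of a female participant's pregnancy, and follow-up of its outcome, to the end of the protocol's post-dose contraception window.
2. Reconcile the two statements of that window (sections 5.1 and 5.6 against 13.4.2 and 13.4.3). The sponsor should decide which one governs; this review does not choose.
3. In 13.4.4, remove the sentence limiting partner collection to TS-161 recipients. Collect partner pregnancies for all men who took study drug, and classify them by treatment and timing after unblinding.

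The cost is an amendment to Appendix D and section 8.7.8, matching consent wording, one end-of-window contact with women of child-bearing potential, and a few extra partner forms. The SAE tail already runs to Day 86, so a single contact at that point would serve both purposes.
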